5.3 Treatment assignment and randomization

Patients will be randomized in a 1:1 ratio to one of the two treatment arms at randomization visit. Randomization will be performed by the use of sealed envelopes. The investigator or his/her delegate will open the sealed envelope after confirming that the patient fulfills all ex- and inclusion criteria. The envelope will assign a randomization number to the patient, which can be used to link the patient to a treatment arm.

The randomization numbers will be generated using the following procedure to ensure that treatment assignment is unbiased and concealed from patients and investigator staff. A patient randomization list will be produced by the provider using a validated system that automates the random assignment of patient numbers to randomization numbers. These randomization numbers are linked to the different treatment arms.

The randomization scheme for patients will be reviewed and approved by a member of the Randomization Group.

At randomization visit an eligible patient will be given the lowest available randomization number. This number assigns the patient to one of the treatment arms. The investigator will enter the randomization number on the case report form (CRF).

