2.8 Additional analysis

In order to explore the additional effect of lifestyle intervention on various related end-points an additional analysis will be performed for PASI 75, PASI 90 & PASI 100 and all the study biomarkers at V9 (Week 16), V12 (Week 28) and end-of-study i.e. Week 56 for both treatment arms, separately based on three below mentioned subgroups:

- Patients with weight loss <5%
- Patients with weight loss $\geq 5\%$ - < 10%
- Patients with weight loss $\geq 10\%$

For all the above mentioned sub-groups no. of patients falling in each sub-group will be descriptively summarized using frequency, percentages and exact 95% clopper-pearson CI at V9 (Week 16), V12 (Week 28) and end-of-study i.e. Week 56 for both treatment arms, separately using FAS. Change in weight loss will be compared from the baseline weight.

All the patients who achieved PASI 75, 90 & 100 at V9 (Week 16), V12 (Week 28) and end-of-study i.e. Week 56 will be descriptively summarized using frequency, percentages and exact 95% CI using clopper-pearson method for the above mentioned sub-groups in both treatment arms, separately using FAS. Further additional analysis will be performed on FAS dataset comparing treatments with respect to the PASI 75, 90 & 100 in a logistic regression model with the factors treatment, center and covariate baseline PASI. The odds ratio and its 95% confidence interval (CI) and p-value will be given. The above analysis will be performed for all the three sub-groups independently.

PASI score at baseline & PASI 75, 90 & 100 scores and biomarkers value will be descriptively summarized using N, n, Mean, median, standard deviation, min, max for all the three subgroups using FAS. All the summary statistics and analysis on biomarkers will be performed

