only for the patients participating in Biomarker substudy. Further, PASI 75, 90 and 100 scores at V9 (Week 16), V12 (Week 28) and end-of-study i.e. Week 56 will be analyzed for all the three sub-groups, separately. Absolute PASI scores will be analyzed using a Mixed Model for Repeated Measurements (MMRM) with factors treatment, center, visit, visit*treatment interaction and covariate baseline PASI. The raw- as well as the adjusted (LS-) means and their differences between treatment groups will be calculated for each visit together with their corresponding 95% confidence intervals and p-values, for all the three sub-groups separately. Also, similar MMRM model will be used for the biomarkers Free fatty acid serum profile, sThy-1, adiponectin, leptin, insulin, HOMA-IR, proinsulin, IL-6, TNF-alpha, M30 assay, IL-1 beta, IL-1Ra, IL-18, IL-18bp, P1NP, CTX, RANKL, OPG, sclerostin, NT-proBNP, CD154, and a 30-panel multiplex inflammatory cytokine and chemokines panel for all the three sub-groups, separately.

All the above mentioned analysis for PASI 75, 90, 100 & all study biomarkers will be performed separately for both treatment groups for below mentioned comparisons:

- a. Patients with weight loss $\geq 5\%$ - $< 10\%$ vs. Patients with weight loss $< 5\%$
- b. Patients with weight loss $\geq 10\%$ vs. Patients with weight loss $< 5\%$

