Evidence on effect size of lifestyle intervention on PASI response is relatively rare and assumptions were based on the following studies: A clinical study by [Al-Mutairi et al \(2014\)](#) showed an absolute increase of 27% in PASI75 response to biologic treatment (Infliximab, Etanercept, Ustekinumab, Adalimumab) in overweight or obese, moderate to severe psoriasis patients undergoing weight reduction compared to patients not undergoing weight reduction. However the dietary regimen used in this study was highly restrictive and consecutively led to a strong mean weight loss (-13 kg vs + 1,5 kg in the control group after 24 weeks). Naldi et al (2014) showed an absolute increase of 6% in PASI75 response to systemic treatment in overweight to obese, moderate to severe psoriasis patients undergoing diet and physical exercise compared to control patients. The lifestyle intervention in this study was less intensive and consecutively led to a smaller mean weight loss (-3kg vs -1.6 kg in the control group after 20 weeks). It seems that the extent of increase in PASI response correlates with the achieved weight loss, at least to a certain extent. PASI90 data were not available for both cited studies. The lifestyle intervention conducted in the present study is less intensive than the one applied by Al-Mutairi et al. but more intensive compared to Naldi et al. A lifestyle intervention very similar to the one applied in our study was previously able to show a mean weight loss of -3.8 kg vs. - 1.4 kg after 1 year (Kulzer B et al., 2014). Maximum weight loss can already be expected after 3-4 month. As part of the lifestyle intervention program activity tracking devices will be used in the present study to further support the lifestyle intervention.

Based on these considerations and the fact that we are looking at PASI90 response in the present study, we assume an absolute increase of 9% in PASI90 response in the Secukinumab combined with lifestyle intervention arm to 90% PASI90 responders compared to 81% PASI90 responders in the Secukinumab alone arm. An absolute increase of 9% in PASI90 responders would also be clinically meaningful.

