Based on these assumptions 342 patients per arm would provide a power of 90 % at a two-sided alpha of 0.05 to demonstrate that the percentage of PASI90 responders at week 28 is higher in the Secukinumab combined with lifestyle intervention arm compared to the Secukinumab alone arm. In case the true effect size would only be 7.5 %, this sample size would still provide a power of 75 %. To compensate for some expected drop out and/or premature discontinuations, 380 patients per arm are planned to be recruited for this study.

4 Change to protocol specified analyses

Below mentioned changes to the analysis described in Section 9 of the protocol version 02 are planned.

- i. Separate analyses will be performed for subjects with fasting and non-fasting status for fasting plasma glucose, fructosamine, and HbA1c in secondary analyses
- ii. Separate analyses will be performed for subjects with fasting and non-fasting status for all the biomarkers in biomarker sub-study
- iii. Additional analysis proposed for stratification of the analysis for PASI 75, PASI 90, PASI 100 and all study biomarkers by the groups “patients achieving weight loss < 5%”, “patients achieving weight loss $\geq 5\%$ - < 10%” and “patients achieving weight loss $\geq 10\%$ ” in each treatment arm.

5 Appendix

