2.6 Additional analysis

In order to explore the additional effect of lifestyle intervention on biomarker sub-study endpoints, an additional analysis will be performed for all the study biomarkers at V9 (Week 16) & V12 (Week 28) for both treatment arms, separately based on three below mentioned subgroups:

- Patients with weight loss $< 5\%$
- Patients with weight loss $\geq 5\% - < 10\%$
- Patients with weight loss $\geq 10\%$

For all the above mentioned sub-groups, the no. of patients falling in each sub-group will be descriptively summarized using frequency, percentages and exact 95% Clopper-Pearson CI at V9 (Week 16) and V12 (Week 28) for both treatment arms, separately using BAS. Change in weight loss will be compared from the baseline weight.

All the patient's biomarkers value will be summarized descriptively using N, n, mean, median, standard deviation (SD), min and max for all the three subgroups using BAS. Absolute biomarker values will be analyzed using a MMRM with factors treatment, center, visit, visit*treatment interaction and covariate baseline biomarker value. The raw- as well as the adjusted (LS-) means and their differences between treatment groups will be calculated for each visit together with their corresponding 95% confidence intervals and p-values, for all the three sub-groups separately. Also, similar MMRM model will be used for all the biomarkers listed in [section 2.5.1](#), for all the three sub-groups, separately.

All the above- mentioned analyses for all study biomarkers will be performed separately for both treatment groups for below mentioned comparisons:

- a. Patients with weight loss $\geq 5\% - < 10\%$ vs. Patients with weight loss $< 5\%$
- b. Patients with weight loss $\geq 10\%$ vs. Patients with weight loss $< 5\%$
- c. Patients with weight loss $\geq 5\% - < 10\%$ vs. Patients with weight loss $\geq 10\%$

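### Treatment arms are compared within bands of post-randomisation weight loss, so the within-band estimates are not randomised comparisons and lose part of any effect that runs through weight loss

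*SAP*

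**What the plan says.** SAP 2.8 sets out to explore what the lifestyle intervention adds. It bands patients by percentage weight loss from baseline at Weeks 16, 28 and 56. For PASI 75, 90 and 100 it specifies a logistic model with treatment, centre and baseline PASI, giving an odds ratio, 95% CI and p-value, and then says "The above analysis will be performed for all the three sub-groups independently". For absolute PASI it specifies an MMRM whose between-arm differences come with "confidence intervals and p-values, for all the three sub-groups separately", and a similar MMRM for the biomarkers.

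Biomarker SAP 2.6 repeats the pattern: "Absolute biomarker values will be analyzed using a MMRM with factors treatment, center, visit, visit*treatment interaction and covariate baseline biomarker value", with arm differences by visit in each band.

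Both sections also list band-versus-band comparisons within each arm: (a) and (b) in SAP 2.8, and (a) to (c) in biomarker SAP 2.6. SAP section 4, item iii, which declares the change from the protocol, describes only a stratification inside each arm. It does not mention arm-versus-arm models within a band.

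Two protocol passages define the role of weight loss. Section 3.6 sets a loss above 5% of baseline weight as the target, which is the first cut-point of the bands. Section 3.3 expects the extent of weight loss to track the fall in inflammation and, through it, psoriasis status.

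**The concern.** Protocol 5.3 says "Patients will be randomized in a 1:1 ratio to one of the two treatment arms at randomization visit". That makes the whole arms comparable. It does not make comparable the subsets picked out later by something the intervention is meant to change. An arm A patient who lost 10% did so without the programme; an arm B patient in the same band had its help. They are likely to differ in whatever else drives weight loss, such as motivation or health.

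Two things follow. First, if any such factor also affects skin response, the within-band contrast is biased, and here against the lifestyle arm. Second, holding weight loss roughly constant removes part of any effect that works through weight loss, which is one of the effects the section says it wants to explore. The report would then carry odds ratios and p-values presented as treatment comparisons that cannot be read that way.

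**Working it through.** **The plan's own figure.** SAP section 3: "we assume an absolute increase of 9% in PASI90 response in the Secukinumab combined with lifestyle intervention arm to 90% PASI90 responders" against 81% alone, and "342 patients per arm would provide a power of 90 % at a two-sided alpha of 0.05". The two-proportion formula with continuity correction gives n = 342 per arm (320 without it). At n = 342 the corrected power is 90.1% for 81% vs 90%, and 74.7% for 81% vs 88.5%, matching the plan's 90% and 75%. With "380 patients per arm are planned to be recruited for this study", 342/380 = 0.90, a 10% allowance. The sample size is sound and does not depend on SAP 2.8.

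**Inputs for the illustration.** From the documents: 81% control response, 380 per arm, and mean losses of 3.8 kg vs 1.4 kg in a similar programme at one year (SAP section 3). Assumed: body weight 90–100 kg, normally distributed percentage loss, SD 4–6 points. The base case is 100 kg (1.4% vs 3.8%) and SD 5.

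**Step 1: band sizes.** Expected count below 5% = 380 × Φ((5 − mean)/SD), and likewise for the other bands. In the base case, arm A: 380 × Φ(0.72) = 290; arm B: 380 × Φ(0.24) = 226.

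| Band | Base case, A / B | Range over 90–100 kg, SD 4–6, A / B |
|---|---|---|
| <5% | 290 / 226 | 272–310 / 210–235 |
| 5 to <10% | 73 / 113 | 64–77 / 103–132 |
| ≥10% | 16 / 41 | 6–30 / 23–64 |

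Treatment itself fills the bands unequally.

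**Step 2: no skin effect, shared cause present.** Let a factor U correlate r with weight loss and carry log-odds ratio g per SD for PASI90. At equal weight loss, the mean of U in arm B is lower by r × (3.8 − 1.4)/SD, because the programme supplied part of the loss. With r = 0.5 and SD 5 the gap is 0.5 × 2.4/5 = 0.24. With g = 0.6 the spurious odds ratio at equal loss is about exp(−0.24 × 0.6) = 0.87. The bands are wide, so the band figures are somewhat closer to 1. Simulation with 2,000,000 patients per arm (overall odds ratio 1.00 each time; runs agree to about 0.01):

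| Shared cause | <5% | 5 to <10% | ≥10% |
|---|---|---|---|
| r = 0 | 1.00 | 1.00 | 1.00 |
| r = 0.3, g = 0.6 | 0.96 | 0.93 | 0.93 |
| r = 0.5, g = 0.6 | 0.93 | 0.88 | 0.89 |
| r = 0.7, g = 0.9 | 0.88 | 0.77 | 0.78 |

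**Step 3: real effect, wholly through weight loss, no shared cause.** With 0.35 log-odds per percentage point lost, response is 81% vs 88.7%. The overall odds ratio is (0.887/0.113)/(0.81/0.19) = 1.84. Within bands it becomes 1.46, 1.06 and 1.09. If the full planned effect (81% vs 90%, odds ratio 2.11) ran through weight loss, the first two bands would show 1.63–1.66 and 1.03–1.10 for SD 4–5. At SD 6 this model cannot reach 90% through weight loss alone.

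**Step 4: sparsity.** The ≥10% band holds 16 + 41 = 57 patients in the base case, and from 6 + 23 = 29 to 30 + 64 = 94 over the range. Protocol section 4 plans about 100 sites, and the SAP 5.2.1 code enters centre as a fixed class effect. Most sites would contribute no patient to this band or patients from one arm only. In the biomarker sub-study (50 per arm), scaling by 50/380 gives about 1–4 vs 3–8 patients in the top band.

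**The case against.** The strongest reply is that little rests on this. SAP 2.8 is an additional, exploratory analysis. The primary test is the unstratified FAS comparison in SAP 2.5.2. Biomarker SAP 2.5.2 disclaims formal hypothesis testing. All of that stands, and it limits the consequence.

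A second reply is that the section is really about within-arm comparisons, as SAP section 4, item iii, suggests. That wording fits the descriptive tables and the band-versus-band comparisons. It does not fit models that carry a treatment factor and report differences between treatment groups. The two places conflict and need reconciling.

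Third, the null bias is small against sampling error. In the base case with r = 0.5 and g = 0.6, approximate 95% intervals around the band odds ratios are 0.61–1.43, 0.38–2.01 and 0.14–5.44, and the chance of p < 0.05 is only about 6%, 6% and 5%. With r = 0.7 and g = 0.9 it is about 10%, 9% and 6%. So a reader might infer that spurious significant harm is likely; it is not.

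Two other strong readings also go too far:
- That banding removes the whole lifestyle effect. In Step 3 most of the odds ratio survives in the <5% band, and effects through other routes, such as the physical activity named in Protocol 1.1 and 3.3, are not removed.
- That the centre-adjusted models cannot be fitted at all. The arithmetic supports this worry only for the ≥10% PASI logistic model; the <5% band would hold about 500 patients. The figure of 100 sites does not carry over to the sub-study, whose number of sites is not stated.

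Finally, without unmeasured common causes the contrast would approximate an effect not transmitted through weight band. That is fair, but the assumption cannot be tested with these data and the plan does not state it.

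**Conclusion.** The point holds as an analysis-choice fault in an exploratory section. The within-band arm contrasts in SAP 2.8 and biomarker SAP 2.6 condition on a consequence of treatment. Their null bias ranges from none (odds ratio 1.00) to about 0.77–0.88, depending on how strongly weight loss and response share causes. They also strip out part, not all, of a weight-mediated effect: about 1.84 becomes 1.46 in the largest band and 1.0–1.1 in the middle one. The ≥10% band is too small for the planned centre-adjusted logistic model. Body weight, SD, the strength of the shared cause and the slope of response on weight loss are assumptions; only the response rate, the arm size and the kilogram losses come from the documents. The primary conclusion and the sample size are untouched, and a reader should not infer otherwise.

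**What to change.** 1. In SAP 2.8 and biomarker SAP 2.6, delete the between-arm logistic and MMRM comparisons within weight-loss bands. Alternatively, report them without p-values and label them as non-causal.
2. Reconcile SAP 2.8 with SAP section 4, item iii, so that both say whether the stratification is within arm only.
3. Keep the within-arm descriptive tables. Label band-versus-band comparisons (a) to (c) as non-randomised associations, adjusted for baseline PASI or baseline marker and for baseline weight.
4. If the share of effect running through weight loss is of interest, an optional mediation analysis on the whole FAS may be added. It must state the assumption of no unmeasured confounding between weight loss and response and include a sensitivity analysis for it, because it depends on the same shared causes that bias the bands.

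Items 1 to 3 cost SAP wording, some relabelling and a covariate; deletion also means fewer tables. Item 4, if taken up, adds programming. No change to data collection or sample size is needed.

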2.11 Interim analysis

A first analysis of the core study (primary, secondary [REDACTED] endpoints related to the core study) will be performed after all subjects have completed the core study.

[REDACTED]

The two analyses will be reported in separate clinical study reports.

3 Sample size calculation

This study is primarily designed to demonstrate superiority of secukinumab combined with lifestyle intervention vs Secukinumab alone in terms of PASI90 response at week 28. A PASI90 response of 81% at week 28 under Secukinumab alone in patients with metabolic syndrome is assumed. This number is based on a retrospective analysis performed with data from the CLEAR study, taking into account the slightly higher BMI of the patient population with metabolic syndrome (BMI 23-42 kg/m², Albareda M et al., 2014) and the open-label design.

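### The within-arm weight-loss comparisons in SAP 2.8 and biomarker SAP 2.6 have no model term that estimates them, omit baseline weight, and should be joined by a continuous weight-change model.

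*SAP*

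**What the plan says.** SAP 2.8 sorts patients by percent weight loss (<5%, 5 to <10%, ≥10%) at weeks 16, 28 and 56. It first compares the arms inside each band. For PASI 75, 90 and 100 it uses a "logistic regression model with the factors treatment, center and covariate baseline PASI"; for absolute PASI it uses an MMRM that adds visit and visit-by-treatment. It then turns to comparisons inside each arm: "All the above mentioned analysis for PASI 75, 90, 100 & all study biomarkers will be performed separately for both treatment groups". These are (a) 5 to <10% against <5%, and (b) ≥10% against <5%. No further model is given, and baseline weight appears only as the reference for calculating loss.

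Biomarker SAP 2.6 follows the same pattern: "analyses for all study biomarkers will be performed separately for both treatment groups for below mentioned comparisons". It adds a third contrast between the two upper bands. The MMRM code in its section 5.1 has treatment, site, visit, their interaction and the baseline marker, and no weight term.

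The link between weight loss and skin response matters to the sponsor's own reasoning. SAP section 3 says: "It seems that the extent of increase in PASI response correlates with the achieved weight loss, at least to a certain extent".

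**The concern.** There are three separate defects.

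1. **Specification.** Applied within one arm, the listed models lose their treatment terms and have no parameter left for (a) or (b). A programmer would have to invent the model.
2. **Efficiency.** The obvious repair is to put band where treatment stood. That cuts a measured continuous variable at 5% and 10%. It pools every loss below 5% with every gain, and each contrast drops one band.
3. **Confounding.** Band is a post-baseline, non-randomised grouping. Baseline weight may relate both to percent loss and to PASI response, and it is already collected but not adjusted for.

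Whether more weight loss goes with better skin is the mechanism behind the trial. P-values are planned for these analyses, so a nearly empty contrast could be read as evidence of no dose-response.

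**Working it through.** **Plan's own figure.** SAP section 3 states "342 patients per arm would provide a power of 90 % at a two-sided alpha of 0.05", with "to 90% PASI90 responders compared to 81% PASI90 responders in the Secukinumab alone arm". The two-proportion formula gives n = [1.96·√(2·0.855·0.145) + 1.2816·√(0.81·0.19 + 0.90·0.10)]² / 0.09² = 319.6. The continuity correction gives (319.6/4)·[1 + √(1 + 4/(319.6·0.09))]² = 341.4, so 342 is reproduced. Power at 7.5 points comes out at 74.7%, against the stated 75%. No power is stated for the SAP 2.8 comparisons.

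**Inputs.**
- From the documents: 342 per arm; PASI90 of 90% (arm B) and 81% (arm A); mean loss of 3.8 and 1.4 kg in a similar programme.
- Assumed: baseline weight near 100 kg, so that kg reads as percent; normal percent loss with SD 4 to 6 points; a linear logit slope β per percentage point. The documents give neither an SD nor a slope.

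**Band sizes.** The ≥10% band holds 342·Φ((3.8 − 10)/5) ≈ 37 patients in arm B. In arm A it holds 342·Φ((1.4 − 10)/5) ≈ 15 with SD 5. With SD 4 it holds about 5, or about 6 if the mean is 1.5.

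**Wald calculation.**
- Continuous term: z = β·√[n(I₂ − I₁²/I₀)], where I_k is the mean of p(1 − p)xᵏ.
- Band contrast: z = (logit q_j − logit q₀) / √[1/(N_j q_j(1 − q_j)) + 1/(N₀ q₀(1 − q₀))].
- Information kept is (z_band / z_cont)².

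Example (arm B, SD 5, β = 0.10, contrast a): response is 87.3% in the <5% band and 93.3% in the 5 to <10% band. The log-odds differ by 0.71 and the standard error is 0.45, so z is about 1.56. The continuous z is 2.68, so information kept is (1.56/2.68)² = 0.34.

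| Arm, SD, slope | Bands | Power: continuous / a / b | Information kept: a / b |
|---|---|---|---|
| B, 5, 0.10 | 203/102/37 | 76 / 34 / 29% | 0.34 / 0.28 |
| A, 5, 0.10 | 261/66/15 | 93 / 47 / 24% | 0.31 / 0.13 |
| A, 4, 0.10 | 279/58/5 | 80 / 35 / 11% | 0.32 / 0.06 |
| B, 5, 0.20 | 203/102/37 | 99.7 / 75 / 42% | 0.30 / 0.14 |
| B, 5, 0.30 | 203/102/37 | 100 / 86 / 33% | 0.26 / 0.06 |

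Over SD 4 to 6, with slopes set to give the continuous term 50 to 90% power, (a) keeps 29 to 41% of the information and (b) keeps 6 to 42%.

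**These figures flatter (b).** At β = 0.10 the ≥10% band has about 37·(1 − 0.958) = 1.6 expected non-responders in arm B and 15·(1 − 0.929) = 1.1 in arm A. In simulation (mean loss 4, SD 5 in B; 1.5, SD 4 in A; odds ratio 1.10 per 1%), the continuous term had 74% (B) and 77% (A) power, and (a) had 30% and 32%. A Wald test of (b) reached about 10% at most at every slope tried. A comparison of proportions for (b) did better in arm B (28%) but had essentially no power in arm A. Center is ignored throughout. With about 100 sites (protocol section 4), one arm has roughly 342/100 ≈ 3 patients per site.

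**Biomarkers.** With 50 per arm, the ≥10% band would hold about 3 to 8 patients in arm B. For correlations of 0.2 to 0.4, (a) keeps 38 to 60% of the power and (b) 47 to 76%, by a normal approximation that is optimistic at these counts.

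**Baseline weight.** Assume no true weight-loss effect, arm B's distribution (mean 4, SD 5), weight SD 20 kg, correlation 0.2 to 0.3 with percent loss, and a PASI90 odds ratio of 0.8 to 0.9 per 10 kg. The expected spurious odds ratios are then 0.84 to 0.95 for (a) and 0.73 to 0.91 for (b). False-positive rates barely move: with correlation ±0.2 and log-odds −0.4 per SD of weight, they are 4 to 6% for (a) and 1 to 7% for (b). With a true slope of 0.09 and correlation +0.2, adjustment raises the power of the continuous term from 54% to 69%.

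**The case against.** **The power loss depends on the slope.** A reader might infer that the comparisons always lose half or more of the power and would usually miss a real dose-response. The documents do not support that. If the planned effect were wholly due to the 2.4 kg difference (3.8 − 1.4), the slope would be (logit 0.90 − logit 0.81)/2.4 = 0.747/2.4 ≈ 0.31 per kg. At an odds ratio of 1.22 per 1% in arm B, simulation gives (a) 85% against 99.9%. The information loss remains, but power is high enough to hide it.

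**A linear truth favours a linear model.** This stands. Protocol 3.6 sets a target above 5% of baseline weight, so asking whether patients who reach it do better is a fair question. With a true step at 5% (assumed odds ratio 3), simulation reverses the ranking: (a) has 63% (B) and 69% (A), against 52% and 39% for the continuous term. A reader might conclude that the bands should be dropped; they should not be.

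**Confounding is modest and its direction is unknown.** SAP section 3 mentions "taking into account the slightly higher BMI of the patient population with metabolic syndrome". A reader might take this to say that higher BMI lowers PASI90, but the sentence gives no direction. The correlation used above is assumed. Adjusting for baseline weight leaves other confounding, such as adherence, in place.

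**The analysis is exploratory.** This also stands. No power or claim attaches to it, and biomarker SAP 2.5.2 disclaims formal testing. SAP 2.7.1 to 2.7.4 cannot be read in the public version, so a continuous weight analysis may exist there. Neither point supplies the missing term in 2.8.

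**Conclusion.** The specification gap is certain from the text: no listed term estimates (a) or (b), and baseline weight is not a covariate, in either SAP.

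The size of the efficiency loss is conditional. With band in place of treatment, a roughly linear relation and SD 4 to 6, each PASI90 contrast gives up at least about 58% of the information at moderate slopes. Contrast (b) is nearly uninformative for PASI90, especially in arm A with about 6 to 15 patients. The power loss in (a) shrinks at steep slopes, and a threshold at 5% would favour the bands. Omitting baseline weight produces a modest bias whose sign depends on an unknown correlation.

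A reader might extend this to the trial's main conclusion. The documents do not support that: the primary model in SAP 2.5.2 does not use weight loss.

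**What to change.** In SAP 2.8, and correspondingly in biomarker SAP 2.6 and its code in 5.1:

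1. Write out the within-arm model for the contrasts, with band in place of treatment.
2. Add baseline weight as a covariate alongside baseline PASI or the baseline marker.
3. Add one model per arm with percent weight change from baseline at that visit as a continuous term and the same covariates: logistic for PASI 75, 90 and 100, and linear or MMRM for continuous outcomes. Include a spline or quadratic check, and name this the main dose-response analysis.
4. Keep the bands for the descriptive tables and for the 5%-target question.
5. Label all these results observational.

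The cost is SAP wording and a little extra exploratory output, using data already collected. The added model assumes linearity, which the spline or quadratic term checks.
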